### 3.6.2. Data Collection and Processing:

Measures will be obtained by trained staff who are blinded to treatment assignment. In-person follow-up data collection visits will be scheduled at gestational Week 32 and Week 36, as well as at 6-weeks, 6-months, and 12-months postpartum. If a study participant has moved out of the local area after enrolling in the study and continues to be a Tricare beneficiary, with the participant's permission, research staff will collect weight data via the participant's Body Trace scale uploads and other data instruments through the use of paper questionnaires mailed to the participant. In addition, telephone interventions will continue as normal per protocol. Relevant incentives (e.g., actual diapers given to participants) will be used to obtain high retention at all follow-up data collection visits. Incentives will not exceed the maximum amount specified by military policy. The diapers are an incentive and would be provided to a participant who attends the following data collection visits:

Year 1 (\$50 limit)	32 week visit	Choice of: \$15 worth of diapers, baby ointment, or wet bag
	36 week visit	Choice of: \$15 worth of diapers, baby ointment, or wet bag
	6 week post-partum visit	Handprint keepsake (\$10)
Year 2 (\$50 limit)	6 month post-partum visit	Choice of: \$15 worth of diapers, baby ointment, or wet bag
	12 month post-partum visit	Choice of: \$15 worth of diapers, baby ointment, or wet bag

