**3.3. Significance; 3.4. Military Relevance; & 3.5. Background and Review of Literature:**

Considerable attention has been given to the alarming prevalence of overweight and obesity in the U.S. population [1]. This epidemic extends to women of childbearing age [1], including women who are active duty personnel in the U.S. military and DoD TRICARE beneficiaries (retirees and dependents). As of 2011, 34% of active duty military women were overweight and 6% were obese [2]. Indeed, excess weight is

associated with \$1.1 billion dollars each year in medical costs in the military health care system [3]. Furthermore, specifically for active duty personnel, excess weight and inadequate fitness are frequent causes for discharge. The military must then recruit and train replacements for about \$50,000 per person, thus spending more than \$60 million a year due to failed first-term enlistees [3]. While the long-term impact of pregnancy on military fitness test performance is unknown, several studies have found that women have significantly lower fitness test scores at 6-months postpartum [4, 5]. Finally, pregravid overweight/obesity has been found to be a key risk factor for perinatal complications in both civilian [6] and military populations [7].

In addition to pregravid weight status, excessive gestational weight gain is another key risk factor for pregnancy and delivery complications (e.g., gestational diabetes, preeclampsia, caesarean delivery) [8-11] and negative health outcomes for infants [6, 10, 12] as well as overweight status later in life [11-14]. Excessive gestational weight gain is also associated with postpartum weight retention [15-19], a key concern for the U.S. military. Thus, gestational weight gain is a critical consideration, because it is a modifiable risk factor that can be addressed upon pregnancy confirmation.

Women are not meeting the Institute of Medicine guidelines for gestational weight gain. Recent research indicates that many pregnant women do not gain within the 2009 Institute of Medicine guidelines; specifically, 53-71% of normal weight women, 77-84% of overweight, and 74-83% of obese women exceeded the Institute of Medicine guidelines [20, 21]. Although there is limited research on excessive gestational weight gain among TRICARE beneficiaries, there is some indication that many active duty women, like the civilian population, are exceeding gestational weight gain guidelines [22].

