**Weight goals:** The GWG goals for each participant will reflect the 2009 IOM guidelines[30]: a) for normal weight women (BMI 18.5-24.9 kg/m^2): 11-16 kgs (25-35 lbs); b) for overweight women (BMI 25.0-29.9 kg/m^2): 7-11.5 kgs (15-25 lbs); and c) for obese women (BMI 30-39.9 kg/m^2): 5-9 kgs (11-20 lbs) based on their weight collected at their screening appointments. Ongoing weight self-monitoring will be a central feature of the intervention at all steps. Most experts considered frequent weighing a key component to any weight management program (83-86) and it appears to be important in pregnancy-related weight interventions as well. For this reason, participants will be prompted to weigh themselves at least weekly on an electronic scale, which they will be given at baseline. The electronic scale will be issued to the subject as part of treatment on a hand receipt. Due to depreciation of the scale over 21 months of use during the study, the scales would be valued at near zero, and therefore subjects will not be required to return them. The electronic scales are part of the treatment and not considered a form of compensation for participating in the study. Each time a participant weighs, the electronic scale will upload the weight automatically to a secure website. Each week, participants will receive an email from their interventionist with a weight graph tailored to their screening weight BMI and their current weight trajectory as well as personalized feedback from their interventionist about their trajectory. Participants who gain less weight than the guidelines will be instructed to increase their caloric intake and to monitor their weight daily. Study staff will notify Obstetrics staff about participants who gain less weight than the guidelines at two consecutive intervention sessions, but will be retained in the study.

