### 3.6.3. Setting:

Subjects will complete pre-screening, consent and data collection in the OB clinics at WHASC and SAMMC. Interventions will be completed via telephone.

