#### **6.1. Outcome Measures:**

The primary study outcomes will be a comparison of GWG from baseline to the final gestational weight (either week 32 or week 36, depending on the delivery date) as well as a comparison of weight loss from 6-week postpartum to 12-months postpartum for the 3 intervention arms.

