#### **6.3. Statistical Analysis:**

All of the analyses will be performed with SASv9.4. Data will be examined for distributional normality and outliers prior to any analyses. Descriptive statistics will be generated for all variables of interest included in the analysis, overall and by treatment arm. Univariate comparisons will consist of t-test, chi-square test, ANOVA, and their respective non-parametric counterparts if needed, for continuous/categorical variables respectively. Primary analyses will be intention-to-treat, without regard to intervention adherence. We will use multivariable linear ANCOVA-like regression models for continuous outcomes, to model and compare

the GWG (Hypothesis 1) and PPWL (Hypothesis 2), in the 3 arms. Using these models, treatment effects will be estimated and tested by comparing change in group-specific means at the final prenatal visit and 12-months postpartum conservatively adjusting for baseline differences (which will be minimal by virtue of randomization) and in the case of hypothesis 2 for 6-weeks postpartum weight differences. Randomization validity will be assessed by comparing arms on baseline measures using chi-square tests, ANOVAs and other appropriate tests. If imbalances are found, we will consider adjusting the between-group analyses for potential confounders.

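### Home-scale weights after a move are collected only from women who keep Tricare, so a woman who moves and loses eligibility has no remote route to the 6- or 12-month weight

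*Combined protocol and SAP*

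**What the plan says.** Section 3.6.2 sets the default: "In-person follow-up data collection visits will be scheduled at gestational Week 32 and Week 36, as well as at 6-weeks, 6-months, and 12-months postpartum". Section 3.6.3 fixes the place: "Subjects will complete pre-screening, consent and data collection in the OB clinics at WHASC and SAMMC".

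Section 3.6.2 also gives the one alternative. It opens with "If a study participant has moved out of the local area after enrolling in the study and continues to be a Tricare beneficiary" and, with the woman's permission, continues: "research staff will collect weight data via the participant's Body Trace scale uploads". Other instruments are mailed. No other section gives a remote route to an outcome weight.

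The postpartum primary outcome in Section 6.1 is "a comparison of weight loss from 6-week postpartum to 12-months postpartum for the 3 intervention arms". On the analysis, Section 6.3 says: "Primary analyses will be intention-to-treat, without regard to intervention adherence". It gives no method for missing outcomes.

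On the scale itself, the weight goals for the GWG intervention in Section 3.6.1 say: "Each time a participant weighs, the electronic scale will upload the weight automatically to a secure website". Scales are issued at baseline and are not returned.

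The background (Sections 3.3 to 3.5) says of active duty personnel that "excess weight and inadequate fitness are frequent causes for discharge".

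**The concern.** The rule makes collection of a primary outcome depend on benefit status. For active duty women, the protocol's own rationale links leaving the service to weight and fitness. If poor postpartum weight contributes to discharge, and discharge to loss of Tricare and a move, then some 12-month weights would be missing because of their likely values. Data observed before the loss might not fully account for that.

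An intention-to-treat comparison needs an outcome, or a stated way of handling its absence, for every randomized woman. The plan has no missing-data method, and this rule gives up weights that may be obtainable. The scale stays with the woman and uploads automatically, and the plan already accepts its readings as outcome weights for other women who move.

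The GWG-only arm has no postpartum intervention. If the postpartum intervention works and weight drives this loss, more of it would fall in GWG-only. That arm would then look better than it is, and the postpartum effect would be understated.

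**Working it through.** **1. Is there another route?** The provisions on postpartum weight, side by side:

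| Woman's situation | Route to the 6- and 12-month weight | Source |
|---|---|---|
| Stays local | In person at the clinics | Sections 3.6.2, 3.6.3 |
| Moves, still a Tricare beneficiary | Home-scale upload, with permission | Section 3.6.2 |
| Moves, no longer a Tricare beneficiary | No remote route; in-person return not barred | No provision found |

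**2. Who is in the third row?** Section 3.6.7 counts active duty women, retirees and dependents as beneficiaries. Leaving the service is therefore not the same as losing Tricare. The row contains only women who both move and lose eligibility before the visit.

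**3. Do the entry criteria prevent moves?** Section 3.6.7 asks for planned local residence of at least 1.5 years, which is 18 months. Section 3.6.4 gives 21 months of participation. The criterion reduces moves, but it records an intention and falls 21 − 18 = 3 months short.

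**4. Size of a possible bias.** The documents give no rate of separation, loss of eligibility or moving, and no SD, so there is no plan figure to reproduce. All inputs here are assumptions. Let p be the share of an arm with a missing 12-month weight for this reason, and d the amount (kg) by which those women lost less weight than the observed women. Then

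- true arm mean = (1 − p) × observed mean + p × (observed mean − d) = observed mean − p × d, so the observed mean overstates loss by p × d;
- shift in the contrast toward zero = (p in GWG-only − p in the PPWL arm) × d.

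| p, GWG-only | p, PPWL arm | d (kg) | Shift toward zero (kg) |
|---|---|---|---|
| 5% | 3% | 3 | 0.02 × 3 = 0.06 |
| 8% | 4% | 4 | 0.04 × 4 = 0.16 |
| 10% | 5% | 6 | 0.05 × 6 = 0.30 |
| 5% | 5% | any, same in both arms | 0 |

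**5. Scale of that shift.** Assume an SD of 4 to 7 kg for weight change and 150 women per arm. The standard error of a two-arm difference is SD × √(2/150) = SD × 0.1155, or 0.46 to 0.81 kg. The shift then runs from 0.06/0.81 = 0.07 to 0.30/0.46 = 0.65 standard errors.

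**6. Effect on power.** Assume two-sided 0.05 and an effect of 0.323 SD, which gives 80% power at 150 per arm. Losing 5% of 12-month weights in each arm lowers power to 78.0%, and losing 10% lowers it to 75.7%. Possible bias is the main reason to act.

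**The case against.** The strongest reply is that the affected group may be very small. It takes a discharge or other loss of eligibility, with no remaining entitlement as a retiree or dependent, and a move, all before 12 months postpartum. The discharge statement is background on active duty personnel in general. It names fitness as well as weight, gives no rate, and says nothing about timing in the first postpartum year. The cohort also includes retirees and dependents, to whom it does not apply. All of this stands.

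A reader might therefore infer too much: that every woman who leaves the service and moves loses her primary outcome, or that the missingness is known to follow weight and to bias the trial toward no effect. The documents support neither. The condition concerns Tricare, not service; an in-person return remains open; and the arm imbalance behind any bias is assumed.

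A second reply is that the remedy is less simple than it looks. Three parts stand:

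- The consent and HIPAA texts are not available here, so permission for contact after benefits end cannot be confirmed.
- Mailing every form would include the Edinburgh depression scale. Section 4.9 has it given in person at 6 and 12 months, with referral to a military service described as available to active duty members.
- The postpartum prompt to weigh at least weekly belongs to the PPWL intervention, so GWG-only uploads may be sparse unless a weight is requested.

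These narrow the fix but do not remove the gap.

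A third reply is that the larger weakness is the missing-data plan itself. Going from 755 enrolled to 450 completing implies 1 − 450/755 = 40.4% non-completion from all causes, some of it perhaps before randomization. That is fair, but it does not justify giving up weights that could be collected.

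**Conclusion.** The gap is real. A stated rule leaves women who move and lose Tricare with no remote route to the 6- or 12-month weight, and the protocol gives no reason why a home-scale weight should depend on benefit status. The protocol's own rationale makes it plausible, for active duty women, that the loss depends on weight or fitness.

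The direction and size of any bias are not established. The 0.06 to 0.30 kg toward zero holds only under the assumed unequal loss and assumed weight differences; equal loss with the same difference gives none. No count of affected women per arm is offered. There is no rate to apply, and the denominator is unsettled: Section 3.6.1 randomizes 450, while Section 6.2 treats 450 as completers. This is a modest but worthwhile correction, justified by its low cost and by the fact that no later analysis can recover a weight that was never collected.

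**What to change.** In Section 3.6.2:

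- Remove Tricare status as a condition for collecting the outcome weight. State that every randomized woman who moves is asked, with her permission, for a home-scale weight at each remaining visit, in all three arms.
- Keep the condition for medical-record and fitness data.
- Before extending mailed instruments to non-beneficiaries, reconcile those that trigger clinical referral, notably the Edinburgh scale, with Section 4.9.
- Record the date and reason for each missing 12-month weight, including loss of eligibility, and report them by arm.

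In Section 6.3, it would help to prespecify a missing-data method with a missing-not-at-random sensitivity analysis for weights that remain missing.

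The cost is one amended sentence, possibly a consent line on contact after benefits end, and some extra calls or messages. The scales are already issued. The trade-off is a home-scale reading in place of the calibrated duplicate weight of Section 3.6.8, which Section 3.6.2 already accepts for other women who move.

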**Weight goals:** Weight loss from birth to 6-weeks postpartum is fairly standard—approximately 6 kilograms (or 13 pounds)—regardless of pregravid weight category and GWG [29]. For women with a normal pregravid BMI, the PPWL goal (initiated at 6-weeks postpartum) will be to return to the pregravid weight. For women who were overweight or obese pre-pregnancy, the PPWL goal (initiated at 6-weeks postpartum) will be to at least return to their pregravid weight and, if desired, lose up to an additional 5% of their pregravid weight. All participants will be advised to lose weight at a rate of approximately 1 pound per week, which has been shown to not have adverse effects on infant growth or breast milk production. All women will be given a tailored graph indicating the recommended PPWL trajectory. They will be prompted to weigh themselves at least weekly on the electronic scale provided at baseline (which will upload the weight automatically to a secure website). The electronic scale will be issued to the subject as part of treatment on a hand receipt. Due to depreciation of the scale over 21 months of use during the study, the scales would be valued at near zero, and therefore subjects will not be required to return them. The electronic scales are part of the treatment and not considered a form of compensation for participating in the study. These weights will be plotted on a graph and emailed to them weekly along

with personalized feedback from their interventionist about their weight trajectory. The graph will clearly identify weight losses that are both greater than recommended and below recommendations. Participants who are losing weight faster than expected will be instructed to increase their caloric intake and to monitor their weight daily. Participants who lose more weight than expected at 2 consecutive monthly intervention sessions will be referred to their obstetrician for guidance, but will be retained in the study.

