### 3.6.8. Instrumentation:

- Contact information
- Demographics: Participants will complete a questionnaire regarding their age, parity, race, and ethnicity.
- Physical Assessment:
  - Weight: At all measurement visits, weight will be recorded in kilograms. Weight will be measured on a calibrated digital scale in duplicate, with the participant wearing light clothing and no shoes. While we will obtain the mother's weight at baseline, we will also obtain self-reported pregravid weight (before the last menstrual period). The difficulty of anticipating when a final weight should be obtained to capture the fullest extent of GWG was considered, and we elected to use an approach that afforded two possible weights that would be available for analytic purposes. The Week 36 weight will be the primary outcome except for mothers who deliver prior to 36 weeks, in which case we will use the Week 32 weight. Thus, we will have a final observation of GWG for all participants, regardless of whether they deliver earlier than 36 weeks.
  - Waist Circumference: As an indicator of subcutaneous and visceral abdominal fat, waist circumference will be measured (recorded in centimeters) using a non-distensible measuring tape and standard protocols for positioning.
  - Height: Height, using a wall-mounted stadiometer, will be recorded in centimeters. BMI will be calculated from measured weight and height.
- Physical Activity: We will assess physical activity, subjectively, using the International Physical Activity Questionnaire, as it has been used in other studies of gestational/postpartum weight management, has been validated against accelerometry, and has good test-retest reliability. We will also assess physical

activity objectively using the Actical accelerometer. Participants will be asked to wear the accelerometer for 7 days, including 2 weekend days and 3 weekdays.

- Weight Gain Recommendations: We will assess knowledge of weight gain recommendations at the Baseline visit, before randomization. One previous study has shown the gestational weight gain expectations, in a civilian population, predicted actual pregnancy weight gain; however, it is not certain whether this finding will replicate in a military population.

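### For women who move, the primary weight comes from treatment-scale uploads, and weighing prompts are written only for arms in active treatment, so its availability, timing and measurement may differ by arm

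*Combined protocol and SAP*

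**What the plan says.** By default, Section 3.6.2 states: "Measures will be obtained by trained staff who are blinded to treatment assignment". Section 3.6.8 gives the method: "Weight will be measured on a calibrated digital scale in duplicate, with the participant wearing light clothing and no shoes".

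For a woman who has left the local area, Section 3.6.2 takes weight from "Body Trace scale uploads and other data instruments through the use of paper questionnaires mailed to the participant". This applies if she "continues to be a Tricare beneficiary, with the participant's permission"; no weight source is given for other movers. The same paragraph keeps telephone intervention sessions running for movers, and the listed incentives are for attending data collection visits.

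The uploading scale belongs to the interventions. In Section 3.6.1, the weight goals of the GWG intervention say: "The electronic scale will be issued to the subject as part of treatment on a hand receipt". They add that "participants will be prompted to weigh themselves at least weekly on an electronic scale, which they will be given at baseline". The weight goals of the PPWL intervention say of those women: "They will be prompted to weigh themselves at least weekly on the electronic scale provided at baseline". The weekly emailed weight graphs are likewise described only within the two interventions.

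GWG treatment runs from randomization to birth in GWG-only and GWG+PPWL. PPWL treatment runs from 6 weeks to 12 months postpartum in PPWL-only and GWG+PPWL. Section 3.6 makes PPWL-only the comparator for gestational gain and GWG-only the comparator for postpartum loss. Section 6.1 defines the primary outcomes as change from baseline to the final gestational weight, and from 6 weeks to 12 months postpartum.

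**The concern.** An upload exists only if the woman steps on the scale. Women in active treatment are prompted at least weekly, receive graphs and keep their calls after moving. In the same window, comparator women have no written prompt. A treated mover will probably have a reading close to the visit date; a comparator mover may have an old one or none.

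If the comparator women who keep weighing themselves differ in weight change from those who stop, the missing outcomes are informative and more frequent in one arm. This falls on the contrasts that test Hypotheses 1 and 2. Sections 3.6.2, 3.6.8 and 6.0 to 6.3 contain nothing to limit it. They set no date window, number of readings or weighing conditions for a remote weight, no common request to weigh, no source flag and no sensitivity analysis. Section 6.3 promises intention-to-treat analysis but gives no missing-data method.

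**Working it through.** The plan states no move rate, upload rate or device offset, so it has no figure of its own to reproduce here. The sample size (150 per group) serves only as a denominator.

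**1. Prompts by outcome window** (Sections 3.6, 3.6.1 and 6.1)

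| Window | Arms with a written weighing prompt | Comparator, no written prompt |
|---|---|---|
| Baseline to Week 36 (or Week 32) | GWG-only, GWG+PPWL | PPWL-only |
| 6 weeks to 12 months postpartum | PPWL-only, GWG+PPWL | GWG-only |

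**2. When moves are likely.** Recruitment is before 12 weeks' gestation, and women must plan to stay in the area for at least 1.5 years, that is 18 months (Section 3.6.7). Assume recruitment at 6 to 12 weeks and 4.345 weeks per month.

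- 12-month visit, delivery at 40 weeks: (40 - 12)/4.345 + 12 = 18.4 months; (40 - 6)/4.345 + 12 = 19.8 months.
- Same visit, delivery at 36 weeks: 17.5 to 18.9 months.
- Week 36 visit: (36 - 12)/4.345 = 5.5 months; (36 - 6)/4.345 = 6.9 months.

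After a term delivery, a woman who just meets the residence criterion can be gone before the Hypothesis 2 endpoint. The Week 36 visit lies well inside the 18 months.

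**3. Missing outcomes.** Let m be the share of an arm that moves and u the share of movers with a usable upload. Missing share = m(1 - u). Assume m = 10-20%, with u = 90% if prompted and 50% if not.

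- Treated arm: 0.10 × 0.10 = 1% to 0.20 × 0.10 = 2%, or 1.5 to 3 of 150 women.
- Comparator: 0.10 × 0.50 = 5% to 0.20 × 0.50 = 10%, or 7.5 to 15 of 150 women.

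Over a wider range (m = 5-20%; u = 90% treated, 60% or 30% comparator) the counts per 150 are 0.75 to 3 against 3 to 21.

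**4. Device offset.** Let b be a constant home-minus-clinic difference. The share of observed end weights that come from a home scale is f = mu/(1 - m + mu). The bias in the arm contrast is b(f_treated - f_comparator).

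- m = 10%: f = 0.09/0.99 = 0.091 and 0.05/0.95 = 0.053; difference 0.038.
- m = 20%: f = 0.18/0.98 = 0.184 and 0.10/0.90 = 0.111; difference 0.073.
- With b = 0.5 to 1 kg: 0.5 × 0.038 = 0.02 kg to 1 × 0.073 = 0.07 kg.
- With equal upload rates the two f values are equal and the bias is zero.
- With the wider ranges in step 3 and b = 0.5-1.5 kg: 0.007 to 0.17 kg.

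For Hypothesis 1 the starting weight is always a clinic weight, so an uploaded end weight always means a change of device. For Hypothesis 2 this happens only if the move follows the 6-week visit; a woman who moved before it has both weights from the home scale.

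**The case against.** The remote-weight rule rescues data that would otherwise be lost, and it is written without regard to arm. Both interventions describe the scale as provided at baseline, so every arm appears to hold one. Four stronger readings are tempting, and the documents do not support them.

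- *The plan prescribes different ascertainment by arm.* It does not. Only the treatment prompts differ. That comparator movers would get no request to weigh is inferred from silence; the plan neither provides for such a request nor rules it out.
- *The remote rule contradicts the outcome definition.* Section 6.1 defines the outcomes by time point and not by device, and the remote rule is an express exception to clinic measurement.
- *The device difference passes straight into the treatment effect.* It enters one woman's change score, but in the arm contrast it cancels when home-scale use is equal and is small otherwise (step 4).
- *Blinding fails for movers.* Uploads are automatic and are assigned to research staff, not to interventionists, so nobody can influence a reading. What stays open is the choice among readings, and the density of the feed may hint at the arm.

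It is also fair to say that no document supports applying the same move rate to Hypothesis 1, and that the direction of any selection is unknown. Self-weighing is itself part of treatment, so extra requests to comparator women are not wholly neutral.

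What remains is that nothing written equalizes the chance of a usable weight near the visit date between prompted and unprompted movers.

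**Conclusion.** The point holds as a foreseeable risk, not as a stated difference between arms. For movers, the plan swaps a blinded, standardized weight for treatment-scale uploads and writes weighing prompts only for the arms under treatment. It adds nothing to offset the resulting imbalance. The exposure is greatest at the 12-month endpoint of Hypothesis 2 and weaker for Hypothesis 1.

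The main consequence is unequal and possibly outcome-related missing data: 1-2% of a treated arm against 5-10% of the comparator if 10-20% move and upload rates are 90% and 50%. The device offset is secondary, at about 0.02-0.07 kg in the contrast for an offset of 0.5-1 kg. The move rate, upload rates and offset are all assumptions, and the direction of bias cannot be stated. That the Body Trace scale is the issued electronic scale is inferred from its upload feature. This does not undermine the design, but it should be changed because the remedy is cheap.

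**What to change.** In Section 3.6.2, state that at each scheduled visit blinded assessment staff ask every mover, whatever her arm, for two home weights on the same day, in light clothing and without shoes, within a fixed window around the visit date. State that only those readings serve as the visit weight.

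Record the source of each weight (clinic or remote). In Section 6.3, pre-specify a sensitivity analysis of both primary outcomes that excludes remote weights. Optionally, take one paired home weight on in-person visit days to check the device offset.

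The cost is one extra message per remote visit, using the scale and website already in place, and a small added weighing prompt to comparator movers. The optional check adds one home weighing on each clinic-visit day used. No treatment content changes.
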